9. EVALUATIONS AND STATISTICAL METHODS

9.1. Evaluations

The following evaluations relating to tolerability, safety and clinical benefit will be made:

1. Adverse events (AEs) suspected to be related to injections of HGF plasmid
2. Discontinuations related to adverse effects from the injections of HGF plasmid
3. All AEs up to Month 3, Month 6, Month 12, and Month 18
4. Serious adverse events (SAEs) up to Month 3, Month 6, Month 12, and Month 18
5. Number of deaths and cause over the 18 month period up to Month 3, Month 6, Month 12, and Month 18
6. Number of subjects in whom the largest ulcer healed completely or gets smaller (photo confirmation) at 6, 12 and 18 months (cumulative)
7. Number of subjects in whom rest pain (based on the 100 mm VAS scale) reduces by 20 mm or more or was completely relieved at 6, 12 and 18 months (cumulative)
8. Change in VascuQol Questionnaire (QOL) score compared to the baseline at 6, 12 and 18 months
9. Number of subjects revascularized (bypass or endovascular intervention) up to Month 3, Month 6, Month 12, and Month 18
10. Number of subjects with minor and number of subjects with major amputations (at or above the ankle) up to Month 3, Month 6, Month 12, and Month 18

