2.5.5 Efficacy Analysis

- Ulcer improvement**

A table showing the number of subjects completely healed in the target ulcer will be provided at up to 6 months, > 6 months to 12 months, from >12 months to 18 months. If available, the number of subjects with at least 20% reduction in bi-dimensional size (by measuring largest diameters) will be provided. The reduction in bi-dimensional size will be calculated by taking the product of the largest diameters for each baseline and postbaseline measurement, then subtracting the baseline result from the postbaseline result.

- Ischemic Rest pain (of the index leg) using a 10 cm VAS scale**

Rest pain severity will be assessed at the specified predetermined time points. Rest pain severity will also be assessed prior to surgical revascularization or major amputation (of the index leg). A table showing the number of subjects reduced by ≥ 20 mm from baseline in VAS score will be provided at up to 6 months, > 6 months to 12 months, from >12 months to 18 months. Summary statistics will be provided for baseline and change from baseline for each visit and LOCF. One sample t-test for change-from-baseline will be performed. If death occurs, the worst score prior to death instead of last observation will be carried forward.

- Hemodynamic Measurements**

Summary statistics will be provided for baseline and change from baseline for hemodynamic parameters (right/left brachial systolic pressure, ankle systolic pressure measured at dorsalis pedis and posterior tibial, toe systolic pressure, calculated ABI, and calculated TBI) by visit. At each visit, only subjects who have a non-missing value at both baseline and the specific visit will be summarized. Two-sided one-sample t-test will be performed for each visit and LOCF.

- Subjects with any worsening CLI event of index leg**

A summary table and listing of worsening CLI-related events of the index leg including any new or worsening events, worsening rest pain, new ulcer or worsening ulcer, new or worsening wound infection, peripheral vascular intervention, complication of a peripheral vascular intervention, cellulitis, and amputation due to worsening CLI will be provided.

- Subjects who either died, had MI, Stroke, revascularization (by surgical bypass, by endovascular intervention, by hybrid procedure), major amputation, or all-cause death**

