A summary table including counts and percentages and a listing will be provided for these parameters for the following time periods: up to Month 6, 0 to Month 12, and 0 to Month 18.

As a supplemental analysis, time to major amputation or death will be performed, and the Kaplan-Meier (KM) estimates with 2-sided 95% confidence interval using Greenwood's formula will be computed up to the end of the study and plotted. If a subject undergoes major amputation followed by death, it will be counted as an event. If a subject does not experience major amputation or death, the subject will be censored at the date of last contact as recorded on the CRFs.

- **Shift from baseline in Rutherford classification**

Shift from baseline in Rutherford classification will be summarized by study visit.

- **Quality of life (QoL)**

Quality of life (QoL) measurements will be assessed using the disease-specific vascular Quality-of-Life questionnaire (VascuQol). The VascuQol contains 5 domains (pain, symptom, activities, social, and emotional functioning), and responses are scored from 0 (lowest QOL imputed after death) to 7 (best QOL, maximum health). Responses are averaged for composite overall and domain-specific scores, giving equal weight to each question and domain. Subjects' data after revascularization or major amputation will be included in the analysis. However, after death, subjects will be scored as 0. For the effect of treatment on individual domains, pain, symptoms, and activity will be considered the most important of the 5 domains.

Summary statistics will be provided for baseline and change from baseline by visit for each score including total and domain scores. At each visit, only subjects who have a non-missing value at both baseline and the specific visit will be summarized, and two-sided one-sample t-tests for the change-from-baseline will be performed for each visit and LOCF.

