2.5.7 Safety Analysis

- **Adverse Events**

Adverse event (AE) data will be collected using the standard AE CRF. All AEs will be coded using MedDRA dictionary version 16.1.

Treatment-emergent adverse events (TEAEs) will be evaluated, and a table showing the number and percentage of subjects with occurrences categorized by System Organ Class and Preferred Term will be provided by causality (relationship to study drug), whether the AE led to discontinuation, and whether the AE was deemed serious. For the causality, "Likely Related" and "Possibly Related" will be classified as "Related," and the most related AE will be summarized if multiple coded AEs occurred for the same subject. AEs that led to discontinuation and those that were deemed serious will be presented in separate columns. If a subject has more than one occurrence of the AE, the subject will be counted once. An additional table will be provided for the total number of AEs occurring during the study, presented by system organ class, causality, and severity, including all AEs, AEs from Day 0 up to Month 3, from Month 3 up to Month 6, from Month 6 up to Month 12, and Month 12 up to Month 18. To take the most conservative approach in categorizing severity during a period, the worst rating reported will be used in the

categorization. For example, if the severity is rated moderate one week and severe another week during the period, severe will be used as the severity rating category over the period.

Death or other serious AE (non-fatal MI or non-fatal stroke) are not in all cases recorded as an adverse event in the AE CRF, but could also be recorded in the outcome of adverse events. For those subjects who either died, had a serious AE, or discontinued participation in the study because of revascularization or other reason, a summary table and a subject line listing will be provided during the periods listed for the previous table along with the post-Month 18 LTFU period up to Month 24, Month 24-30 and Month 30-36.

- **Laboratory Data**

Listings of subjects with abnormalities will be provided with abnormal values flagged.

The following clinical laboratory tests will be listed:

- Hematology: including hemoglobin, hematocrit, RBC count, WBC count (total and differential) and platelet count.
- Urinalysis: including protein, glucose, blood, ketones, bilirubin, and microscopic examination.

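### The SAP event table has no Month 3 period and no separate minor-amputation row, so six of the twelve counts promised in protocol 9.1 items 9 and 10 are not tabulated

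*SAP*

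**What the plan says.** Protocol 9.1 opens its list with a commitment: "The following evaluations relating to tolerability, safety and clinical benefit will be made". Item 9 is "Number of subjects revascularized (bypass or endovascular intervention) up to Month 3, Month 6, Month 12, and Month 18". Item 10 asks for two separate amputation counts at the same four cut-offs: "Number of subjects with minor and number of subjects with major amputations (at or above the ankle) up to Month 3", then Months 6, 12 and 18. Item 10 does not restrict the limb.

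The event table in SAP 2.5.5 counts subjects who died, or who "had MI, Stroke, revascularization (by surgical bypass, by endovascular intervention, by hybrid procedure), major amputation, or all-cause death". Its periods are "up to Month 6, 0 to Month 12, and 0 to Month 18". Minor amputation is not among its outcomes.

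Two other SAP outputs come close. The worsening-CLI table in 2.5.5 is limited to the index leg and ends its list with "complication of a peripheral vascular intervention, cellulitis, and amputation due to worsening CLI will be provided". It gives no amputation level and no time periods. The adverse event section, 2.5.7, does use a Month 3 boundary ("AEs from Day 0 up to Month 3, from Month 3 up to Month 6"), but for adverse events. A companion table over the same periods covers death, serious adverse events and discontinuation.

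**The concern.** In a single-arm study that declares itself descriptive, the pre-listed counts are the result. A statistician who programs the SAP as written will not produce some of them. The opening paragraph of the SAP says that it adds detail to the protocol's analysis, and the SAP flags no departure. A reader of the report could not tell whether the counts were dropped on purpose or overlooked. Section 2.5.7 keeps a Month 3 boundary for adverse events, which makes an oversight the likelier explanation.

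Two things are at stake.

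- **Minor amputation.** This is a tissue-loss outcome in the treated limb. Protocol 8.1.2 generally sends index-limb interventions for worsening CLI to the CLI section of the CRF, not to the adverse event form. If the event table omits minor amputation, the adverse event tables will usually not show it either.
- **Month 3.** The earliest event period in the SAP runs to Month 6. By then both four-set blocks of the first cycle have been given, the second ending at Month 3 + 42 days, so the table has no earlier view of revascularization or major amputation.

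**Working it through.** There is no sample size, power or error-rate figure to reproduce. The check sets each count required by items 9 and 10 against every SAP table that could hold it.

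**Required:** 3 outcomes x 4 cut-offs = 12 counts.

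| Outcome | Month 3 | Month 6 | Month 12 | Month 18 |
|---|---|---|---|---|
| Revascularization | missing | given | given | given |
| Major amputation | missing | given | given | given |
| Minor amputation | missing | missing | missing | missing |

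**Given by the SAP event table:** 2 outcomes x 3 periods = 6.

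**Missing:** 1 (revascularization, Month 3) + 1 (major amputation, Month 3) + 4 (minor amputation, all cut-offs) = 6. All six come from one absent column and one absent row.

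**Do other SAP tables fill the gap?**

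- *Worsening-CLI table (2.5.5).* It has one amputation item for the index leg, with no level and no periods. It cannot give minor amputation by cut-off.
- *Adverse event table by period (2.5.7).* It counts events, not subjects, by system organ class, causality and severity. Non-index-limb amputations do reach the adverse event form (Protocol 4.13 and 8.1.1), but this table would not identify them as amputations. Index-limb events generally stay off the form.
- *Table of death, serious adverse events and discontinuation (2.5.7).* It has a Month 3 period, but captures revascularization only where it led to discontinuation.
- *Kaplan-Meier analysis (2.5.5).* Its endpoint is major amputation or death combined. The composite can be read at Month 3; major amputation alone cannot.
- *Baseline summary (2.5.2).* The SAP's explicit mention of minor amputation in its analyses is here, as history of the index limb.

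**Where would a Month 3 cut fall?** Table 1 of both documents puts the first block at Days 0, 14, 28 and 42. A month is 30 days, so Month 3 is Day 90, which is 90 - 42 = 48 days after the nominal end of that block and the first dosing day of the next. The Month 3 visit may take place on Days 83 to 97 (90 ± 7). The Month 3 analysis window in Protocol 9.2.3 and SAP 2.4.3 is Days 80 to 100. If events were counted to Day 100, between 100 - 97 = 3 and 100 - 83 = 17 days could follow the Month 3 dose. Protocol 9.2.3 states an event cut-off day for Month 12 (Day 395) and Month 18 (Day 593), but none for Month 3.

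**The case against.** The strongest reply is that little is lost. The event table and the worsening-CLI table each come with a listing, SAP 2.4.1 promises listings behind every table, and SAP 2.4.3 says that study day will be shown for events. With about 8-10 subjects, a reader can count Month 3 events by eye. This stands for revascularization and major amputation. It is weaker for minor amputation: the event listing covers only the table's own outcomes, and the worsening-CLI listing helps only if it shows amputation level, which the SAP does not promise.

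It is also fair to say that six of twelve overstates the scale, since two small omissions produce all six, and that no estimate or test changes. Both points stand and keep the matter minor.

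A reader might infer more than the documents support:

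- *That whole outcomes are lost.* Revascularization and major amputation are tabulated at Months 6, 12 and 18, and deaths have a Month 3 period in 2.5.7. Minor amputation is the only outcome without a row of its own.
- *That Month 3 marks the end of the first four-set block and isolates it cleanly.* That block ends at Day 42, Month 3 opens the next, and the analysis window can run past the Month 3 dose.
- *That the SAP pools minor with major amputation.* The worsening-CLI item is unsplit, but the SAP does not say how its rows will be laid out, and major amputation is reported separately in the event table.
- *That index-limb amputation never reaches the adverse event form.* Protocol 8.1.2 excepts events of unexpected speed or extent, or with a strong temporal relation to the product.

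**Conclusion.** The mismatch is real and small. Six of the twelve counts in Protocol 9.1 items 9 and 10 have no place in the SAP tables: revascularization and major amputation at Month 3, and minor amputation at every cut-off. The other six are produced. Some of the missing counts can be rebuilt from listings, provided that event days, and for minor amputation the level, are shown.

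No inference is affected. With 8 to 10 subjects, one event moves a percentage by 1/10 = 10 to 1/8 = 12.5 points, so the tables will be read as counts of individuals. The reason to act is that safety is a primary objective and the protocol listed these counts in advance. The conclusion assumes that the protocol list is binding, as its wording indicates, and that the SAP tables will be programmed as described.

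**What to change.** In the SAP 2.5.5 event table:

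1. Add a cumulative Day 0 to Month 3 column. State the event cut-off day and how it relates to the Month 3 dose, for example whether events on or after the actual date of that dose are counted.
2. Add a minor-amputation row for any limb, with index and non-index legs shown separately. A row limited to the index leg would be narrower than item 10. State the limb scope of the major-amputation row in the same way.
3. Extend the accompanying listing to minor amputations, with limb, level and study day.

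If the sponsor prefers the present table, the SAP should state the departure from Protocol 9.1 and give the reason.

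The cost is one column, one row and a footnote. The data are already collected: Protocol 4.9 and 8.1.2 place index-limb amputations and revascularizations in the CRF, and 8.1.1 places non-index amputations on the adverse event form. The only extra work is to draw the minor-amputation row from both CRF sections.

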2.5.6 PK Analyses

A listing with summary statistics (n, mean, SD, min, and max) will be provided for Serum HGF protein, and a listing of PCR for HGF plasmid DNA Assays will be provided.

For Anti-HGF antibody and confirmation from fusion test, the antibody indication (Yes/No) and fusion test result (Yes/No, if available) will be presented on one listing.

2.5.7 Safety Analysis

- **Adverse Events**

Adverse event (AE) data will be collected using the standard AE CRF. All AEs will be coded using MedDRA dictionary version 16.1.

Treatment-emergent adverse events (TEAEs) will be evaluated, and a table showing the number and percentage of subjects with occurrences categorized by System Organ Class and Preferred Term will be provided by causality (relationship to study drug), whether the AE led to discontinuation, and whether the AE was deemed serious. For the causality, "Likely Related" and "Possibly Related" will be classified as "Related," and the most related AE will be summarized if multiple coded AEs occurred for the same subject. AEs that led to discontinuation and those that were deemed serious will be presented in separate columns. If a subject has more than one occurrence of the AE, the subject will be counted once. An additional table will be provided for the total number of AEs occurring during the study, presented by system organ class, causality, and severity, including all AEs, AEs from Day 0 up to Month 3, from Month 3 up to Month 6, from Month 6 up to Month 12, and Month 12 up to Month 18. To take the most conservative approach in categorizing severity during a period, the worst rating reported will be used in the

categorization. For example, if the severity is rated moderate one week and severe another week during the period, severe will be used as the severity rating category over the period.

Death or other serious AE (non-fatal MI or non-fatal stroke) are not in all cases recorded as an adverse event in the AE CRF, but could also be recorded in the outcome of adverse events. For those subjects who either died, had a serious AE, or discontinued participation in the study because of revascularization or other reason, a summary table and a subject line listing will be provided during the periods listed for the previous table along with the post-Month 18 LTFU period up to Month 24, Month 24-30 and Month 30-36.

- **Laboratory Data**

Listings of subjects with abnormalities will be provided with abnormal values flagged.

The following clinical laboratory tests will be listed:

- Hematology: including hemoglobin, hematocrit, RBC count, WBC count (total and differential) and platelet count.
- Urinalysis: including protein, glucose, blood, ketones, bilirubin, and microscopic examination.
- Blood chemistry: glucose (fasting), uric acid, total cholesterol, HDL, calculated LDL, triglycerides, aspartate transaminase (AST), alanine aminotransferase (ALT), calcium, phosphorus, total bilirubin, alkaline phosphatase, total protein, albumin, globulin, lactic acid dehydrogenase (LDH), serum creatinine, creatinine clearance (estimated using the Cockcroft-Gault formula), blood urea nitrogen (BUN), and electrolytes (Na^+ , K^+ , Cl^-).

- **Physical Examination**

The number of subjects with abnormalities will be provided for the following visit windows: Day 0 to Day 42, Month 3 to Month 3+42 Days, Month 6, Month 9 to Month 9+42 Days, Month 12 to Month 12+42 Days, Month 15, and Month 18/ET. A listing of subjects with abnormalities will be presented.

- **Retinopathy Examination**

Summary statistics will be provided for baseline and change from baseline for Early Treatment Diabetic Retinopathy Study (ETDRS) score by visit. At each visit, only subjects who have a non-missing value at both baseline and the specific visit will be summarized. The number and percent of normal, abnormal (clinically significant, not clinically significant, and all) retinopathy examinations will be presented for baseline, Month 12, and Month 18. A listing of ETDRS scores and abnormalities will also be provided.

AnGes

AMG0001 Protocol AG-CLI-0209
STATISTICAL ANALYSIS PLAN, FINAL Ver. 1

Statistical Analysis Plan Signature Page

This Statistical Analysis Plan has been prepared in accordance with team reviewers' specifications.

Document Authors		
[name] Project Statistician PharPoint Research, Inc.	SIGNATURE:  DocuSigned by:  [name] Signer Name: [name] Signing Reason: I approve this document Signing Time: 22-Mar-2018 11:37 AM EDT 4AB99FDC32904E00AB3D4FED13A6402C	Date (ddmmmyyyy) 22-Mar-2018 11:37 AM EDT
[name] AnGes USA Statistics AnGes USA Inc.	SIGNATURE: 	Date (ddmmmyyyy) 2 April, 2018
Review/Approvals		
[name] Reviewing Statistician PharPoint Research, Inc.	SIGNATURE: 	Date (ddmmmyyyy) 22 Mar 2018
[name], MS Director of Clinical Operations AnGes USA Inc.	SIGNATURE: 	Date (ddmmmyyyy) 22 March 2018
[name] [name], MPH Managing Director AnGes USA Inc.	SIGNATURE: 	Date (ddmmmyyyy) 22 March 2018

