3.1. Study Population

Subjects (40-90 years old) with Chronic Critical Limb Ischemia who have:

Severe ischemic pedal rest pain (nocturnal metatarsalgia, Rutherford 4) in the index lower limb with ankle and/or toe systolic pressures of less than 50 and 30 mmHg, respectively, classical features of rest pain and on opioids for pain relief. Classical features include pedal pain that is severe and typically occurs at night when the limb is no longer in a dependent position but in severe cases can be continuous. The pain is localized in the distal part of the foot. Partial relief may be obtained by the dependent position whereas cold and elevation of the lower limb aggravates the pain. Severe pain responds only to opioids.

OR

Ischemic ulcers /gangrene (Rutherford 5) in the affected lower limb with ischemic ulcer measurements ≤ 20 cm² in area (≤ 10 cm² for ischemic ulcers at the heel) for the largest ischemic ulcer with or without rest pain, and ankle and/or toe pressures less than 70 and 50 mmHg, respectively.

IN ADDITION, SUBJECTS WILL HAVE:

No option for revascularization by endovascular intervention or bypass surgery (see definitions below).

No option is defined as the inability to receive an endovascular intervention or surgical bypass procedure due to inflow, conduit or outflow reasons or due to a severe and irreversible co-morbidity.

OR

Poor option (high risk) for revascularization by surgery (see definition below) but no option for revascularization by an endovascular procedure (Type D lesions or worse using the TASC II classification).¹

Definition for poor option (high risk) for revascularization surgery:

Anatomic

- Need for a tibial level synthetic or cryopreserved bypass
- Need for use of great saphenous vein < 3 mm in diameter for tibial level bypass based on venous duplex ultrasound
- Need for use of spliced vein or single piece of non-great saphenous vein < 3 mm in diameter, for tibial level bypass
- Distal target unsuitable for bypass, e.g. < 2 mm in diameter or circumferentially calcified

¹Norgren, L., Hiatt, W.R., et al., Inter-Society Consensus for the Management of Peripheral Arterial Disease (TASC II), Eur J. VascEndovascSurg, Vol 33, S1-S70; 2007.

- Open lower extremity wound that would preclude construction of bypass

OR

Medical

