4.3. Physical Examination

A complete general physical examination of the skin and major body systems (Eyes, Ears, Nose and Throat; Cardiovascular; Respiratory; Gastrointestinal; Musculoskeletal/Connective Tissue; Neurological; Endocrine/Metabolic; Hematopoietic/Lymphatic; Genitourinary) will be completed as part of the study procedures.

Any suspicious lesion found on the skin during the physical examination at Screening should be evaluated by a Dermatologist.

An abbreviated physical exam does not evaluate all systems, but those systems for which exams are deemed medically necessary based on symptoms (symptom-driven exam).

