Physical Examination	X(1)	X(2)	X(2)	X(2)	X(1)	X(2)	X(2)	X(2)	X(1)	X(1)	X(2)	X(2)	X(1)	X(2)	X(2)	X(2)	X(2)	X(1)	X(1)	
Peripheral Vascular Intervention History/Update	X(3)*	X(3)	X(3)	X(3)	X(3)	X(3)	X(3)	X	X(3)	X(3)	X(3)	X(3)	X(3)	X(3)	X(3)	X(3)	X(3)	X	X	
CLI Assessment (7)	X*	X	X	X	X	X	X	X	X	X	X	X	X	X	X	X	X	X	X	
Ulcer Tracings	X(4)*																			
Ulcer Photography (7)	X(4)*	X(6)	X(6)	X(6)	X(6)	X(6)	X(6)	X(6)	X(6)	X(6)	X(6)	X(6)	X(6)	X(6)	X(6)	X(6)	X(6)	X(6)	X(6)	
Retinopathy Examination															X				X	
Study product Administration	X	X	X	X	X	X	X	X	X	X	X	X	X	X	X	X	X			
Injection Site Photography	X	X	X	X	X	X	X	X	X	X	X	X	X	X	X	X	X			
Angiogram Assessment (7)															X					
TcPO2 (7)	X(3)			X(3)					X(3)	X(3)					X(3)			X	X	
Hemodynamic Measurements (7)	X(3)*			X(3)					X	X(3)					X(3)			X	X	
QOL (EQ-5D5L) (7)	X(3)*			X(3)					X	X(3)					X(3)			X	X	
VAS (pain scale) (7)	X(3)*			X(3)					X	X(3)					X(3)			X	X	
Urine Pregnancy	X(5)			X(5)						X(5)					X(5)					
Hematology, Chemistry, & CBC	X(3)			X(3)					X	X(3)					X(3)			X	X	
Urinalysis Collection	X(3)			X(3)					X	X(3)					X(3)			X	X	
Anti-HGF Antibodies Assay	X(3)			X(3)					X	X(3)					X(3)			X	X	
Adverse Events Review (7)	X	X	X	X	X	X	X	X	X	X	X	X	X	X	X	X	X	X	X	
Concomitant Medication Review (7)	X	X	X	X	X	X	X	X	X	X	X	X	X	X	X	X	X	X	X	

* Investigator must confirm stability of CLI prior to dosing between Day -2 and Day 0. These items must be submitted to the Adjudication Committee as a third party confirmation of CLI stability.

(1) Complete physical exam should be performed. If a dosing visit, perform prior to dosing.

(2) Abbreviated physical exam should be performed. If a dosing visit, perform prior to dosing.

(3) Prior to dosing.

(4) Stability of CLI (≥ 2 weeks between the screening and the Day 0 assessments) and subject's ulcers should be confirmed prior to dosing, the subject must have a photo of the largest ulcer on the index leg as well as a photo(s) of the entire index leg to show all ulcer/gangrene locations. Tracings should be taken of the largest ulcer on the index leg only. These must be submitted to the Adjudication Committee. Debridement must be performed prior to these evaluations;

(5) Urine pregnancy tests will be performed prior to dosing on all women aged 55 years or less. For women who have been determined as premenopausal and are not surgically sterile, per the study requirements, will continue with the scheduled urine pregnancy testing throughout the course of the study.

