- (4) Ulcer healing of the largest ulcer on the index limb (determined at Screening) will be assessed clinically by the Investigator by direct visual inspection at each study visit. If the largest ulcer on the index leg heals during the study period the subject should be brought and re-evaluated 2 weeks after healing to confirm it has remained healed and ulcer photography must be completed at that time.
- (5) Photos of largest ulcer on the index leg as well as a photo or photos (if necessary) of the entire index leg to show all ulcer/gangrene locations. Debridement should be performed prior to these evaluations, if necessary.
- (6) Conduct pre-dose when obtained during a dosing visit.
- (7) Procedure must be performed prior to a planned interventional treatment (revascularization or amputation) while on study.
- (8) Urine pregnancy tests will be performed prior to dosing on all women aged 55 years or less. For women who have been determined as premenopausal and are not surgically sterile, per the study requirements will continue with the scheduled urine pregnancy tests throughout the course of the study.
- (9) Performed on all women under the age of 55
- (10) Complete physical exam should be performed. If a dosing visit, perform prior to dosing.
- (11) Abbreviated physical exam should be performed. If a dosing visit, perform prior to dosing.

Schedule of Sample Collection for the Serum HGF Protein & PCR for HGF Plasmid Assays

Study Day	Day 0	Day 4	Day 14	Day 28	Day 42	Month 3	Month 3 + 14 Days	Month 3 + 28 Days	Month 3 + 42 Days	Month 6	Month 9	Month 9 + 4 Days	Month 9 + 42 Days	Month 12	Month 12 + 4 Days	Month 12 + 42 Days	Month 15
Serum HGF protein Assay	X*	X	X*	X*	X*	X*			X*		X*			X*	X		X
PCR for HGF plasmid DNA Assay	X*	X	X*	X*	X*	X*	X*	X*	X*	X	X*	X**	X*	X*	X	X*	X

*At Dosing Visits (indicated by the shaded column), two (2) samples should be drawn one pre-dose and a second drawn four (4) hours post dosing.

**The first 5 subjects who are enrolled will have a blood sample drawn for HGF Plasmid DNA sampling 4 days following their Month 9 Visit.

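### The physical-examination table in SAP 2.5.7 pools the pre-dose Day 0 exam with the Day 14 to 42 exams and has no baseline row, so it cannot separate pre-existing from new findings (minor)

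*SAP*

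**What the plan says.** SAP 2.5.7, Physical Examination, plans one summary: "The number of subjects with abnormalities will be provided for the following visit windows: Day 0 to Day 42". The remaining windows in that sentence are given as "Month 3 to Month 3+42 Days, Month 6, Month 9 to Month 9+42 Days, Month 12 to Month 12+42 Days, Month 15, and Month 18/ET". The SAP also plans to list abnormal findings by subject. No Screening or Baseline row is named, and the count is not restricted to new findings.

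On the Day 0 exam, the note to the SAP schedule (section 2.2) reads: "Complete physical exam should be performed. If a dosing visit, perform prior to dosing". Protocol Table 3, note 1, says the same, and Protocol 5.3.1 lists the exam among the pre-dosing procedures. For Days 14, 28 and 42, Protocol Table 3 carries the note "2) Abbreviated physical exam should be performed. If a dosing visit, perform prior to dosing". Protocol 4.3 defines that kind of exam: "An abbreviated physical exam does not evaluate all systems, but those systems for which exams are deemed medically necessary based on symptoms (symptom-driven exam".

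A Screening exam is also done (Protocol 5.1), but it falls in none of the windows.

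**The concern.** A safety summary of examination findings is read for what changed after treatment began. Here the first row combines an exam that precedes all study product with three that follow the first dose. A subject who is abnormal at Day 0 counts in that row whatever Days 14 to 42 show. Later rows again count every abnormality, and there is no pre-dose figure to set beside them. The study is single-arm, so no control group can supply the reference.

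The population makes this more than a formality. Everyone has critical limb ischemia. One of the two entry routes is "Ischemic ulcers /gangrene (Rutherford 5) in the affected lower limb with ischemic ulcer measurements" up to a size limit, and the other is severe rest pain. Protocol 4.3 includes the skin and the cardiovascular system in the complete exam. Findings before the first dose are therefore likely to be common, although the documents give no rate.

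**Working it through.** The plan gives no figure to reproduce. The check sets the windows against the timing of the exams and then illustrates the effect.

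**1. What the first window contains**

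| Visit | Relation to first injection | Type of exam | Source |
|---|---|---|---|
| Day 0 | before | complete | Protocol 5.3.1 and Table 3 note 1; SAP 2.2 schedule note 10 |
| Day 14 | after (before that visit's dose) | abbreviated | Protocol 5.5 and Table 3 note 2 |
| Day 28 | after (before that visit's dose) | abbreviated | same |
| Day 42 | after (before that visit's dose) | abbreviated | same |

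One of the four exams is pre-treatment, and it is the only complete one.

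**2. All windows.** There are seven: Day 0 to 42; Month 3 to 3+42 days; Month 6; Month 9 to 9+42 days; Month 12 to 12+42 days; Month 15; Month 18/ET. None is purely pre-treatment. The later dosing windows also open with an exam before that visit's dose, but those exams follow earlier dosing. Only the first window mixes untreated with treated.

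**3. The documents' own conventions**
- SAP 2.4.3 places a measurement made on the reference date (Day 0) on the pre-treatment side, and SAP Table 2 has separate Screening and Day 0 analysis visits.
- Protocol 8.2.1 defines a treatment-emergent event as one absent at baseline, or present and worsened.
- The retinopathy paragraph directly after the physical-examination paragraph reports baseline, Month 12 and Month 18.

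The physical-examination table follows none of these.

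**4. Illustration.** Let *n* be the number of subjects, *p* the share abnormal at Day 0, and *q* the share of the remaining subjects who become abnormal on Days 14 to 42. Only *n* (about 8 to 10) comes from the documents; *p* and *q* are assumptions. For a single any-abnormality count:

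- expected first-row count = *n*[*p* + (1 − *p*)*q*]
- part that is new = *n*(1 − *p*)*q*
- chance that at least one subject is counted from the Day 0 exam alone = 1 − (1 − *p*)^*n*

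| *n* | *p* | *q* | First row | Of which new |
|---|---|---|---|---|
| 8 | 0.3 | 0 | 8 × 0.30 = 2.4 | 0 |
| 8 | 0.3 | 0.2 | 8 × (0.30 + 0.14) = 3.52 | 1.12 |
| 10 | 0.5 | 0 | 10 × 0.50 = 5.0 | 0 |
| 10 | 0.5 | 0.2 | 10 × (0.50 + 0.10) = 6.0 | 1.0 |
| 8 | 0.8 | 0.2 | 8 × (0.80 + 0.04) = 6.72 | 0.32 |

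The chance that at least one subject is counted from Day 0 alone is 1 − 0.7^8 = 0.94 for *n* = 8, *p* = 0.3. It is practically 1 for *p* = 0.8.

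The same row can arise in different ways. With *n* = 10, a row of 6 fits *p* = 0.6, *q* = 0 (no new cases) as well as *p* = 0.5, *q* = 0.2 (one new case). The table gives no means of telling these apart.

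**The case against.** The best reply is that nothing important depends on this table.

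- **Adverse events.** Protocol 8.2.1 sends physical-examination findings to the adverse event CRF and defines treatment-emergent against baseline. SAP 2.5.7 tabulates those events by system organ class, causality and seriousness, and all events by period and severity.
- **Index leg.** Worsening CLI is generally kept out of adverse event reporting (Protocol 8.1.1), but SAP 2.5.5 plans a table and listing of new or worsening ulcer, infection, cellulitis and amputation, together with ulcer healing and the shift in Rutherford class.
- **Listing.** SAP 2.4.1 puts a listing behind every table, and 2.4.3 says study day will be shown for assessments. With 8 to 10 subjects it can be read in full.
- **Weight.** Examination counts are not among the ten evaluations in Protocol 9.1, and the analysis is descriptive.

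All of this stands and sets the severity. It does not make the summary table readable.

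Three stronger readings are tempting, and the documents do not support them:

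- A reader might infer that the SAP reports pre-existing findings as on-treatment ones. It does not; it calls these only visit windows. The defect is the mixing.
- A reader might infer that every subject is abnormal in the first row before dosing, 8 of 8 to 10 of 10. That requires an all-Rutherford 5 sample and ulcers scored as examination abnormalities. Rutherford 4 subjects are also eligible, no mix is stated, and ulcers have their own assessment and photography.
- A reader might infer that a new finding in a subject abnormal at Day 0 never changes the table. That holds for a single any-abnormality count. The SAP does not say whether counts are by body system; if they are, a new finding in another system changes another cell.

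**Conclusion.** The point holds, and it is minor. As specified, the summary table cannot separate abnormalities present before the first injection from those found afterwards, in the first window or in later ones. This follows from the stated windows and exam times alone and needs no assumed rate. How many subjects in the first row would be pre-existing cannot be derived from the documents; the counts above rest on assumed rates of 30% to 80% abnormal at Day 0. It is also plausible, but not established, that most first-row findings would come from the complete Day 0 exam.

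It would go too far to conclude that the trial cannot show new physical findings. The adverse event tables, the worsening-CLI table and the listing provide other routes to them. No inference is at risk, because the study is not powered for any.

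**What to change.** In SAP 2.5.7, Physical Examination:

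1. Add a Baseline row from the Day 0 pre-dose exam, using Screening if Day 0 is missing.
2. Start the first post-dose window at Day 14, so that it runs from Day 14 to Day 42.
3. In each window after baseline, add the number of subjects with an abnormality in a body system that was normal at baseline. Keep the any-abnormality count beside it.
4. Do not add a worse-than-baseline count unless the CRF grades examination findings; the documents describe no such grading.
5. Footnote that the Day 14, 28 and 42 exams are abbreviated.

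The cost is SAP wording and a table shell. The scheduled exams already supply the data, with no new visit or procedure. There is one small downside: the Day 14 to 42 row would rest only on symptom-driven exams, so its any-abnormality count is not directly comparable with a complete baseline exam and could look like improvement. The footnote is there to prevent that reading.
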